5.1.4. Duration of Response

Duration of response (DOR) is defined as the time from the date of the first response (CR or PR), whichever is recorded first, to the date of progressive disease (PD). Duration of response is only defined for patients who have a best overall response of CR or PR using the method of Kaplan-Meier. Confirmation of the response must be performed no less than 4 weeks (28 days) after the criteria for response are first met. The first date at which a CR or PR response was noted will be used to calculate DOR, not the date of the confirmatory tumor assessment.

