11.4. Efficacy

Objective response rate (ORR) - The best OR will be determined by the Investigator for each patient as either CR, PR, SD or relapsed disease/PD. Objective responses for patients in the dose escalation phase will be summarized by dose cohort assigned as well as the dose at which the response occurred. Responses will be tabulated separately for expansion cohorts 1-4. For each expansion cohort, the response rate will be calculated as the number of CR or PR divided by the number of response evaluable patients. To meet the definition of response-evaluable, patients must have undergone radiographic assessment at baseline, received at least one dose of IMGN853, and must have had at least one post-dose tumor assessment.

Duration of Response (DOR) – DOR, defined as the time from initial response until progressive disease, will be estimated for all patients who achieve a confirmed objective response (PR or CR) using the method of Kaplan-Meier. Results will be summarized by dose cohort assigned as well as the dose at which the response occurred.

Progression Free Survival (PFS) – PFS, defined as the time from initiation of study drug until progressive disease or death whichever occurs first, will be estimated using the Kaplan-Meier method. Results will be summarized by dose cohort.

Time to Progression (TTP) - TTP defined as the time from initiation of study drug until progressive disease, will be estimated using the method of Kaplan-Meier. Results will be summarized by dose cohort.

For DOR, PFS, and TTP calculations, subjects not achieving the endpoint will be censored at the time of the last endpoint assessment. Median response times and associated 95% CIs will be presented for descriptive summaries.

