5.1.3. Progression Free Survival (PFS)

PFS is defined as the time from the date of the first dose of study drug until the date of progressive disease or death from any cause, whichever occurs first. PFS is defined based on radiological assessments and determined by the investigator. Clinical progression is not considered a progression endpoint. PFS will be calculated using the following:

- Patients who did not die or have PD will be censored at the date of their last radiological assessment.
- Patients who had PD or death after missing two or more consecutive radiological assessments (PD or death date – last radiological assessment date +1 >=105 days) will be censored at the last adequate radiological assessment.
- Patients who had no baseline or post-baseline radiological assessment(s) will be censored on Day 1 unless the patient died within 105 days of Day 1; in that case, the patient will be considered as having an event at the date of death.
- Patients who started a new anti-cancer therapy prior to documented PD or death will be censored at the last radiological assessment prior to initiation of new anti-cancer therapy.
- When an analysis cutoff date is implemented, only data (deaths and radiological assessments) occurring on or prior to the cutoff date will be used for analysis.

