5.1.5. Time to Progression

Time to progression (TTP) is defined as the time from the date of the first dose of study drug until the date of progressive disease. TTP is defined based on radiological assessments and determined by the investigator. Clinical progression is not considered a progression endpoint. TTP will be censored as follows:

- Patients who did not have PD will be censored at the date of their last radiological assessment.

- Patients who had PD after missing two or more consecutive radiological assessments (PD date – last radiological assessment date +1 >=105 days) will be censored at the last adequate radiological assessment.
- Patients who had no baseline or post-baseline radiological assessment(s) will be censored on Day 1.
- Patients who started a new anti-cancer therapy prior to documented PD will be censored at the last radiological assessment prior to initiation of new anti-cancer therapy.
- When an analysis cutoff date is implemented, only radiological assessments occurring on or prior to the cutoff date will be used for analysis.
- Patients who died prior to PD will be censored at the last radiological assessment.

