5.2.3. DOR

DOR will be reported in listings for all patients and will be tabulated separately for each group with medians and 95% confidence intervals.

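### Duration of response ends only at PD, so a responder who dies without documented PD is censored and the Kaplan-Meier DOR estimate is biased upward

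*SAP*

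**What the plan says.** **DOR event.** SAP 5.1.4 starts the clock at the first CR or PR, "whichever is recorded first, to the date of progressive disease (PD"). Protocol 11.4 agrees: "DOR, defined as the time from initial response until progressive disease". Neither document makes death a DOR event.

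**DOR censoring.** SAP 5.1.4 gives no rule. The only one that reaches DOR is in Protocol 11.4: "For DOR, PFS, and TTP calculations, subjects not achieving the endpoint will be censored at the time of the last endpoint assessment".

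**PFS.** SAP 5.1.3 runs PFS "until the date of progressive disease or death from any cause, whichever occurs first". There are two relevant exceptions. "Patients who had PD or death after missing two or more consecutive radiological assessments" are censored, where the test is that the event date minus the last scan date plus 1 is at least 105 days. Also, "Patients who started a new anti-cancer therapy prior to documented PD or death will be censored at the last radiological assessment" before that therapy.

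**TTP.** SAP 5.1.5 states its treatment of death openly: "Patients who died prior to PD will be censored at the last radiological assessment". SAP 5.1.4 has no matching sentence for DOR.

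**Reporting.** SAP 5.2.3: "DOR will be reported in listings for all patients and will be tabulated separately for each group with medians and 95% confidence intervals". No sensitivity analysis for DOR is planned.

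**The concern.** Kaplan-Meier treats a censored patient as someone who could still progress later, at the same rate as those still under observation. A responder who has died cannot. Censoring that death removes a terminal event from the curve and gives the patient's remaining weight to longer responders, so the curve sits too high as a description of how long responses last.

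Such deaths are plausible here. Cohort 1 allows up to five prior regimens, Cohorts 3 and 4 have no upper limit, and Cohort 5 requires three or four (Protocol 3.1). For platinum-resistant disease on single-agent chemotherapy, Protocol 1.3.1 gives median survival of about 11 months against response durations of 4 to 8 months. Responders who stop drug for reasons other than PD are scanned only every 12 weeks ±3 weeks (Protocol 10.8; Appendix A, note j), which leaves long gaps in which death can come before a documented PD.

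At stake is the reading of the DOR median and of DOR beside PFS: one death can end a patient's PFS and leave the same patient's response counted as ongoing at the last scan.

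**Working it through.** The documents state no target DOR, event count or power for DOR, so there is no figure to reproduce. The check has two parts: following one death through the rules, and sizing the effect.

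**1. One death, four rules.** Take a responder who dies without documented PD.

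| Endpoint | Treatment of the death | Source |
|---|---|---|
| DOR | censored at last assessment | SAP 5.1.4 with Protocol 11.4 |
| TTP | censored at last scan | SAP 5.1.5 |
| PFS | event, if (death - last scan + 1) is below 105 days and no new therapy came first; otherwise censored | SAP 5.1.3 |
| OS | event | SAP 5.1.8 |

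**2. Size under constant hazards.** Let m be the median time from response to PD or death, and f the share of first events that are deaths without PD. The documents do not give f; I assume 5% to 30%.

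- Total hazard: λ = ln 2 / m. PD hazard: λ(1-f).
- With deaths censored, Kaplan-Meier targets exp(-λ(1-f)t), whose median is ln 2 / [λ(1-f)] = m/(1-f).

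| f (assumed) | 1/(1-f) | Median if m = 4 months | m = 6 | m = 8 |
|---|---|---|---|---|
| 5% | 1.05 | 4.21 | 6.32 | 8.42 |
| 10% | 1.11 | 4.44 | 6.67 | 8.89 |
| 20% | 1.25 | 5.00 | 7.50 | 10.00 |
| 30% | 1.43 | 5.71 | 8.57 | 11.43 |

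The values of m span the 4 to 8 months in Protocol 1.3.1 and serve only as a scale.

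**3. With scans every 6 weeks.** Simulation of 20,000 responders with exponential times, m = 6 months, PD dated at the next scan, and deaths censored at the last scan for the PD-only rule:

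| f | 6-month DOR, death an event | 6-month DOR, PD only | Median, death an event | Median, PD only |
|---|---|---|---|---|
| 5% | 0.527 | 0.545 | 6.9 | 6.9 |
| 10% | 0.526 | 0.564 | 6.9 | 6.9 |
| 20% | 0.524 | 0.603 | 6.9 | 8.3 |
| 30% | 0.514 | 0.633 | 6.7 | 9.7 |

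The curve rises at every f. The PD-only median can fall only on a scan date, so it stays put at 5% and 10% and then jumps a whole interval.

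**4. A small sample.** Ten responders have first events at 2, 3, 4, 5, 6, 7, 8, 9, 10 and 12 months. With all ten as events, S(6) = 5/10, so the median is 6. Now let the events at 3 and 5 months be deaths, censored there for simplicity:

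- S(2) = 9/10 = 0.900
- S(4) = 0.900 × 7/8 = 0.788
- S(6) = 0.788 × 5/6 = 0.656
- S(7) = 0.656 × 4/5 = 0.525
- S(8) = 0.525 × 3/4 = 0.394

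The median becomes 8.

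**5. How many patients.** At the illustrative 20% response rate in Protocol 11.1, a 40-patient cohort has 0.20 × 40 = 8 responders, so one such death is 1/8 = 12.5% of them. The pooled EOC group (Cohorts 1, 3 and 5: 40 + 20 + 40 = 100) has about 20, so f = 10% means 2 patients.

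**The case against.** The best defence is that PD-only DOR is a coherent choice. The protocol and SAP agree on it, TTP follows the same convention, and PFS and OS pick up the deaths. DOR is a descriptive secondary endpoint: the primary endpoints are MTD and RP2D, no hypothesis is tested, and no sample size depends on DOR. Responders will be few, so the confidence interval may be wider than the shift. The listings in SAP 5.2.8 show DOR, OS and the censoring, so an affected patient can be found.

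Much of this stands. It limits the consequence but does not remove the bias in the planned summary, and TTP already provides a PD-only measure.

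Four stronger readings are tempting, and the documents do not support them:

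- *The protocol and SAP conflict.* They do not; they share the definition.
- *Every such death is a PFS event.* It is not when the 105-day rule or new therapy intervenes.
- *Clinical progression is excluded from DOR as well.* That exclusion is written for PFS and TTP only (SAP 5.1.3, 5.1.5). SAP 5.1.4 is silent, and Protocol 8.14 lets the investigator determine progression from clinical deterioration.
- *The reported median will be inflated by 11% or 25%.* Those figures need an assumed f of 10% or 20% and continuous exponential times; on the 6-week scan grid the median did not move at 5% or 10%.

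Copying the PFS rules across unchanged would also be a mistake. The bullet that censors at Day 1 cannot apply to responders, who have scans by definition. Off treatment, one scan at the end of its permitted window comes 12 + 3 = 15 weeks = 105 days after the last. The SAP formula then gives 105 + 1 = 106, which meets the cut-off, so a PD found at the very next scheduled scan would be censored as if two scans had been missed.

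**Conclusion.** The point holds as a weakness of definition. As written, a responder's death without documented PD is censored in DOR, and the Kaplan-Meier estimate is biased upward relative to time to PD or death. Under constant hazards the median is inflated by 5% to 43% for an assumed f of 5% to 30%. With 6-week scans the 6-month estimate rises by about 0.02 at f = 5% (0.545 - 0.527) and 0.08 at f = 20% (0.603 - 0.524), while the median may stay put for f up to about 10%. If such deaths are rare the effect is small. No alpha, power or primary endpoint is affected. The change is worth making because it is cheap and removes a known direction of bias.

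**What to change.** In SAP 5.1.4 and Protocol 11.4, define DOR as the time from first response to PD or death from any cause, whichever is first. Write censoring rules for DOR into SAP 5.1.4:

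- No PD or death: censor at the last radiological assessment.
- New anti-cancer therapy before PD or death: censor at the last radiological assessment before that therapy.
- Missed assessments: set a limit that one off-treatment scan at 12 weeks + 3 weeks cannot trigger.
- Leave out the Day 1 bullet used for PFS.

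PD-only DOR may be kept as a labelled sensitivity analysis; TTP stays PD-only in any case.

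The cost is a few sentences. The dates of death are already needed for PFS and OS, and SAP 1.1 allows changes until database lock. The downside is that the reported DOR median may be shorter.

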5.1.5. Time to Progression

Time to progression (TTP) is defined as the time from the date of the first dose of study drug until the date of progressive disease. TTP is defined based on radiological assessments and determined by the investigator. Clinical progression is not considered a progression endpoint. TTP will be censored as follows:

- Patients who did not have PD will be censored at the date of their last radiological assessment.

- Patients who had PD after missing two or more consecutive radiological assessments (PD date – last radiological assessment date +1 >=105 days) will be censored at the last adequate radiological assessment.
- Patients who had no baseline or post-baseline radiological assessment(s) will be censored on Day 1.
- Patients who started a new anti-cancer therapy prior to documented PD will be censored at the last radiological assessment prior to initiation of new anti-cancer therapy.
- When an analysis cutoff date is implemented, only radiological assessments occurring on or prior to the cutoff date will be used for analysis.
- Patients who died prior to PD will be censored at the last radiological assessment.

5.1.6. Time to Response

Time to response (TTR) is defined as the time from the date of the first dose of study treatment until the date of the first observed CR or PR. TTR is only defined for subjects who have confirmed CR or PR. TTR will be reported in listings for all patients and summarized for each of the expansion cohorts with medians and 95% confidence intervals for the medians will be presented for TTR for the expansion cohorts.

5.1.7. CA-125 Response

A CA-125 response is defined as a $\geq 50\%$ reduction in CA-125 levels from baseline. The response must be confirmed and maintained for at least 28 days. The baseline sample must be ≥ 2.0 times the upper limit of normal (ULN) and within two weeks prior to starting treatment. The date of response corresponds to the date when the CA-125 level is first reduced by 50%. The summary table for CA-125 will be based on CA-125 evaluable population for the expansion cohorts only.

5.1.8. Overall Survival

Overall survival (OS) is defined as the time from the date of the first dose of study treatment until the date of death from any cause. Patients who are still alive at the time of the analysis will be censored at the last known time alive.

5.2. Analysis of Efficacy Outcomes

5.2.1. ORR

Responses will be tabulated separately for each group with medians and 95% confidence intervals.

5.2.2. PFS

The PFS will be reported in listings and tabulated separately for each group with medians and 95% confidence intervals.

5.2.3. DOR

DOR will be reported in listings for all patients and will be tabulated separately for each group with medians and 95% confidence intervals.

5.2.4. TTP

TTP will be reported in listings for all patients and will be tabulated separately for each group with medians and 95% confidence intervals.

5.2.5. TTR

TTR will be reported in listings for all patients and will be tabulated separately for each group with medians and 95% confidence intervals.

5.2.6. OS

OS will be reported in listings for all patients and will be tabulated separately for each group with medians and 95% confidence intervals.

5.2.7. Subgroup Analysis of Efficacy Outcomes in EOC Expansion Cohorts

Efficacy outcomes will be analyzed for EOC expansion cohorts (1, 3, and 5) on the following patient subgroups:

- Patients who are platinum resistant in EOC expansion cohorts 1, 3, and 5.
- Patients who are platinum resistant in EOC expansion cohorts 1, 3 and 5 by number of prior regimens (1-3 vs >3).
- Patients who are platinum resistant in EOC expansion cohorts 1, 3 and 5 by FR α percent staining at intensity 2+ (PS2) (25-49%, 50-74%, 75-100%, and 50-100%).
- Patients who are platinum resistant in EOC expansion cohorts 1, 3, and 5 by number of prior regimens and FR α percent staining at intensity 2+ (1-3 priors and PS2 \geq 50%, 1-3 priors and PS2 is 25-49%, >3 priors and PS2 \geq 50%, >3 priors and PS is 25-49 %).

Kaplan-Meier plots for PFS will be generated for the above subgroup analyses.

5.2.8. Efficacy Data Listings

Efficacy data listings will include:

- All lesion assessments (target lesion, non-target lesion, new lesion)
- Investigator's RECIST assessments
- CA-125 results
- derived parameters for CA-125 response, BOR, PFS, TTP, DOR, TTR and OS
- censoring for time-to-event variables

6. SAFETY ANALYSES

Safety analyses will use data from the Safety population. Patients will be analyzed according to the actual study treatment received.

6.1. Exposure

Exposure to IMGN853 will be summarized with descriptive statistics for the number of doses received, the number of cycles received, duration of dosing (weeks, calculated as [date of last dose – date of first dose + 21]/7 for Schedule A, and [date of last dose – date of first dose + 14]/7 for Schedule B), total cumulative dose (mg), dose intensity (mg/kg AIBW Q3W, calculated as [total cumulative dose (mg) / {baseline AIBW (kg) * duration of dosing (weeks)/3}]), and relative dose intensity (%), calculated as [dose intensity/ 6] *100).

The number of infusions with dose decreased, infusions interrupted, and dose delayed will also be summarized by cohort. The number of infusions with the rate of infusion decreased will also be summarized by cohort.

Listings will be provided with the information from all of the study drug administration eCRFs. A further listing reporting the exposure measures above will be provided.

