2.3.1.2. Schedule B

IMGN853 administered on Days 1, 8, and 15, with cycles repeating every 28 days.

The starting dose of IMGN853 for Schedule B was 1.1 mg/kg, which was 1/3 the 3.3 mg/kg dose level deemed clinically safe in 9 patients dosed at that level in Schedule A. All patient doses were calculated according to AIBW. Patients were enrolled in cohorts of 3 to 6 patients.

The initial planned doses for Schedule B dose escalation are shown in Table 3. If additional dose exploration was required to define the MTD then dose escalation could proceed at increments $\leq 25\%$. The CRC determined the magnitude of the dose escalation increments following review of available clinical and PK data from patients treated in the current cohort.

Table 3: Initial Planned Dose Levels for Schedule B

Dose Level	Dose (mg/kg) ^a	Percent Increase From Previous Dose Level	Number of Patients (Planned)
1	1.1	N/A	3 or 4-6
2	1.8	65%	3 or 4-6
3	2.5	40%	3 or 4-6
4	3.3	32%	3 or 4-6

^a Patients were dosed based on AIBW

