2.4.1.2. Schedule B

Patients received infusions of IMGN853 as a single agent on Days 1, 8, and 15 of each planned 28-day cycle. A delay of 1 day in the doses received on Days 8 and 15 was permitted; if a delay occurred, each subsequent dose in that cycle was shifted by 1 day. Intervals of < 7 days between each dose were not permitted. The start of the next cycle remained the same.

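### SAP 6.1 adds a fixed 14 days after the last Schedule B dose, which fits a last dose on Day 15 but not on Day 1 or Day 8, so duration and dose intensity are off for patients who stop mid-cycle.

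*SAP*

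**What the plan says.** SAP 6.1 (Exposure) gives one duration formula per schedule: "date of last dose – date of first dose + 21]/7 for Schedule A" and "date of last dose – date of first dose + 14]/7 for Schedule B". Neither depends on where in the cycle the last dose fell, and the SAP does not say what the added days represent.

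Dose intensity, in mg/kg AIBW per three weeks, uses that duration as its denominator: "total cumulative dose (mg) / {baseline AIBW (kg) * duration of dosing (weeks)/3". Relative dose intensity then divides by a single constant: "dose intensity/ 6] *100".

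SAP 2.3.1.2 gives the Schedule B pattern: "IMGN853 administered on Days 1, 8, and 15, with cycles repeating every 28 days". SAP 2.4.1.2 repeats it and adds two timing rules: "Intervals of < 7 days between each dose were not permitted" and "The start of the next cycle remained the same".

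Protocol 5.7.1.2 allows a Day 8 or Day 15 dose to be omitted when retreatment criteria are not met. Protocol 4.1.1 plans 25 Schedule B escalation patients.

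**The concern.** On Schedule A the 21 added days are the gap to the next planned dose after every dose. On Schedule B the gap is 7 days after Day 1, 7 days after Day 8 and 14 days after Day 15. A constant of 14 therefore matches one of the three possible last doses.

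A last dose on Day 1 or Day 8 can occur, because doses can be omitted, treatment stops at a dose-limiting toxicity (Protocol 5.9.3) and patients may withdraw at any time (Protocol 5.10). Such a patient gets a wrong duration, and the error carries into dose intensity and relative dose intensity, both in the cohort summaries and in the patient listing that SAP 6.1 calls for.

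**Working it through.** **Inputs.** The formulas are from SAP 6.1 and the dosing days from SAP 2.3.1.2 and 2.4.1.2. The illustrative dose is 2.0 mg/kg AIBW (Protocol synopsis), with no missed doses. The permitted one-day delay is ignored.

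**Plan's own constants.** Schedule A at 6 mg/kg, one dose: (0 + 21)/7 = 3 weeks; dose intensity 6/(3/3) = 6.0; relative 100%. Six doses: (105 + 21)/7 = 18 weeks; 36/(18/3) = 6.0. The 21 works for every Schedule A dose. On Schedule B, 14 reproduces as Day 15 to Day 29, so complete cycles come out at 28 days each.

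**Schedule B by last dose.** For cycle k the last dose falls L = 28(k − 1) + 0, 7 or 14 days after the first. SAP duration is (L + 14)/7. Duration to the next planned dose is (L + g)/7, with g = 7, 7 or 14. Cumulative dose and AIBW are the same in both, so the ratio of dose intensities (SAP to next-dose) is (L + g)/(L + 14) and does not depend on the dose level.

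Dose intensity (DI) is in mg/kg per 3 weeks.

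| Last dose | L | SAP weeks | Next-dose weeks | SAP DI | Next-dose DI | Ratio |
|---|---|---|---|---|---|---|
| Cycle 1 Day 1 | 0 | 2 | 1 | 3.00 | 6.00 | 7/14 = 50% |
| Cycle 1 Day 8 | 7 | 3 | 2 | 4.00 | 6.00 | 14/21 = 67% |
| Cycle 1 Day 15 | 14 | 4 | 4 | 4.50 | 4.50 | 28/28 = 100% |
| Cycle 2 Day 1 | 28 | 6 | 5 | 4.00 | 4.80 | 35/42 = 83% |
| Cycle 2 Day 8 | 35 | 7 | 6 | 4.29 | 5.00 | 42/49 = 86% |
| Cycle 3 Day 1 | 56 | 10 | 9 | 4.20 | 4.67 | 63/70 = 90% |
| Cycle 3 Day 8 | 63 | 11 | 10 | 4.36 | 4.80 | 70/77 = 91% |
| Cycle 6 Day 1 | 140 | 22 | 21 | 4.36 | 4.57 | 147/154 = 95% |

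**Alternative reading, to the end of the cycle.** The add-on would be 28, 21 or 14 days. Cycle 1 Day 1: 4 weeks, 2.0/(4/3) = 1.5, against the SAP's 3.0. Cycle 1 Day 8: 4 weeks, 4.0/(4/3) = 3.0, against 4.0. The constant again fits only Day 15, but duration is now too short and dose intensity too high.

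**Check of the +7 add-on.** The planned full-cycle rate is 3 × 2.0/(4/3) = 4.5. A patient with no missed dose who stops after Cycle 1 Day 1 or Day 8 gets 6.0 with +7, or 6.0/4.5 = 133% of that rate. Changing the add-on without changing the comparator is therefore not enough.

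**Omitted dose.** Suppose Day 15 of Cycle 1 is omitted and treatment ends. With +7 after Day 8 the interval is 14 days, with 4.0 mg/kg delivered and 4.0 planned: 100%, and the missed dose disappears. Extending the interval to cover Day 15 gives 28 days, 4.0 delivered of 6.0 planned: 67%.

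**The case against.** The strongest reply is that the SAP never defines the add-on. On Schedule A, 21 days is both the gap to the next dose and the end of the cycle, so it cannot separate the two readings; nor can 14 days after Day 15. This stands, and it limits what can be said about direction. A reader might infer that the SAP always understates dose intensity in mid-cycle stoppers. That holds only on the next-dose reading. What survives is that 14 fits neither reading for Day 1 or Day 8.

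A second reply is that one constant, exact for completed cycles, is a fair simplification, and that +7 alone can be worse. Against the 4.5 full-cycle rate, the SAP gives 4.0 (89%) at Cycle 1 Day 8 and 4.29 (95%) at Cycle 2 Day 8; +7 gives 6.0 (133%) and 5.0 (111%). At Cycle 2 Day 1, +7 is closer (4.8, 107%, against 4.0, 89%). It can also hide an omitted dose. This is correct, and it is why the remedy must also change the comparator and handle omitted doses.

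A third reply concerns consequences. A reader might infer that the Schedule A versus B exposure comparison is distorted. SAP 6.1 plans descriptive summaries and no formal comparison, and Schedule B had already been discontinued under Amendment 10. A reader might also infer that those affected are mainly patients stopping for toxicity or early progression; the documents do not say why patients stop mid-cycle. Number of doses, number of cycles and cumulative dose are reported too, and dosing records are listed, so the figures can be recomputed.

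**Conclusion.** The point holds as a small error in a derived exposure variable. On the next-dose convention, a last Schedule B dose on Day 1 or Day 8 makes duration exactly 7 days too long, and dose intensity is 50% to 91% of its value over Cycles 1 to 3, reaching about 95% by Cycle 6. On the cycle-end convention the same patients are still wrong, in the opposite direction. Last doses on Day 15 are unaffected on either.

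The percentages assume nominal dosing days and no missed doses. The reach is descriptive tables and listings for those of about 25 planned patients whose last dose was Day 1 or Day 8; the documents do not give that number.

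The divisor of 6 is a separate matter. It gives a fully dosed 2.0 mg/kg Schedule B patient ending on Day 15 a relative dose intensity of 4.5/6 = 75%, even though the duration is right.

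**What to change.** In SAP 6.1:

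1. State that the days added after the last dose are the interval to the next planned dose. Keep 21 for Schedule A. For Schedule B add 7 when the last dose was a Day 1 or Day 8 dose, and 14 when it was a Day 15 dose.
2. Compute Schedule B relative dose intensity as delivered dose divided by the dose planned over the same interval. A patient who received every planned dose then shows 100% wherever treatment stopped, and early stoppers are not pushed above plan.
3. If a Day 8 or Day 15 dose was omitted before treatment stopped, extend the interval to cover that dose and count it as planned but not given.

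The cost is one conditional and a planned-dose derivation in the exposure program, plus a few lines of SAP text. No new data are needed, and SAP 1.1 allows changes until database lock.
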